### Subgroup analyses:

The tabular summaries described above for plasma biomarkers only will be repeated by subgroup. However, the subgroup analyses will only be conducted if there are a minimum number of subjects in each treatment group/subgroup level:

- If less than 10 subjects fall into any one treatment group/level of a subgroup, then the corresponding summary/analysis for that subgroup will not be conducted.
- If at least 10 subjects fall into all treatment groups/levels of the subgroup, then the corresponding summary/analysis for that subgroup will be conducted.
- These rules will be applied separately for the subgroup analyses which compare individual CT1812 dose groups vs. placebo and for those which compare the pooled CT1812 dose group vs. placebo. It is possible that these criteria will not be met for the analysis based on individual CT1812 dose groups, but once the CT1812 dose groups are pooled, the criteria are met.

The subgroups of interest for plasma biomarkers are:

Subgroup	Definition/Levels
MMSE at Baseline	18-24, 25-27
Amyloid positivity at Baseline	
The C2N Amyloid Probability Score 2 (APS2) in plasma will be used. The APS2 score will be calculated (by C2N) at screening/baseline in plasma.
 
If the APS2 is >47.5, the participant will be included in the amyloid-biomarker positive subgroup. Otherwise, the participant will be included in the amyloid-biomarker negative subgroup. If a participant does not have the APS2 score available, then classification will be based on the plasma pTau217/Tau217 ratio only. If the pTau217/Tau217 ratio is >4.2, the participant will be included in the amyloid-biomarker positive subgroup. Otherwise, the participant will be included in the amyloid-biomarker negative subgroup.
 
Note: The APS2 score is an output that takes into account plasma pTau217/Tau217 and the Aβ42/40 ratio to predict the presence of brain amyloid >25 centiloids via PET.

Skin biopsy sum total composite score at Baseline	
Positive: Baseline skin biopsy sum total composite score >0
 
Negative: Baseline skin biopsy sum total composite score =0

### Figures:

Spaghetti plots displaying individual subject-level data of observed values over time for each plasma biomarker by treatment group (placebo, CT1812 100mg, CT1812 300mg) will be provided.

Line plots displaying the mean ( $\pm$  SD) observed values over time (all time points, including baseline) for each plasma biomarker by treatment group (placebo, CT1812 100mg, CT1812 300mg, Pooled CT1812 100mg+300mg) will be provided.

Line plots displaying the mean ( $\pm$  SD) change from baseline values over time for each plasma biomarker by treatment group (placebo, CT1812 100mg, CT1812 300mg, Pooled CT1812 100mg+300mg) will be provided.

Line plots displaying the LSM ( $\pm$ 95% CI) change from baseline values for each plasma biomarker by treatment group (placebo, CT1812 100mg, CT1812 300mg, Pooled CT1812 100mg+300mg) will be provided.

Vertical scatter plots displaying the individual subject-level data of change from baseline values at Day 98 and Day 182/End of Study for each plasma biomarker by treatment group (placebo, CT1812 100mg, CT1812 300mg) will be provided.

### Listings:

All individual subject-level plasma and CSF biomarker data will be presented in data listings.

## 14. SKIN BIOPSY DATA ANALYSES

### 14.1 Observed Change from Baseline of the Sum Total Composite Score

Sum Total Composite Score is derived at each visit across the 3 biopsy sites for each subject. It is calculated as the sum of the posterior cervical P-SYN composite score, the distal thigh P-SYN composite score, and the distal leg P-SYN composite score. Assuming the subject had all 3 sites biopsied, the sum total composite score has a range of 0 to 36. If a subject is missing one or two of the biopsy site composite scores, then the sum total composite score is calculated as the sum of the available scores which are then stretched/scaled to fit the 0-36 range. If a subject is missing all three biopsy site composite scores, then the sum total composite score is left as missing. The summary table will present descriptive statistics for the observed value at each visit (baseline and end of study), the change from baseline to end of study, and then an ANCOVA analysis comparing the change values for each dose group vs. placebo. The ANCOVA model as described in Section 13.2 should include the baseline sum total composite score as a covariate.

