10.4 Syn-One Test™ Skin Biopsy

Using biopsy kits provided by CND Life Sciences, Inc. (CND), punch biopsies will be taken to assess presence of phosphorylated alpha-synuclein. The biopsy will be performed during the screening period once all other screening procedures are complete with this procedure to occur at least 24 hours before the Baseline visit. Three-millimeter punch biopsies will be taken from the distal leg, the distal thigh, and the posterior cervical region after local anesthesia with 1% lidocaine. Given the national lidocaine shortage, suitable substitutes are lidocaine with epinephrine (1.0% or 2.0% lidocaine with 1:100,000 epinephrine), lidocaine without epinephrine, or bupivacaine.

Any subject with a history of reaction to local anesthetic will be exempt from the procedure.

Any subject that as previously had a Syn-One Test™ does not need to have this procedure repeated. Results from this biopsy will be entered into the eCRF by the site staff.

Any subject that was randomized into the study prior to the implementation of the Syn-One Test™ is exempt from this procedure.

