### 3.3 Exploratory Objectives

- To evaluate the efficacy of 2 doses of once-daily oral CT1812, administered for 6 months in subjects with DLB.
- To evaluate the change in  $\alpha$ -synuclein pathology in skin biopsies over the course of 6 months.

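### Skin-biopsy composite is rescaled separately at each visit, so a site missing at one visit can show change when no site score has changed

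*SAP*

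**What the plan says.** - **Objective.** SAP 3.3 lists, as exploratory, the change in alpha-synuclein "pathology in skin biopsies over the course of 6 months".
- **Score.** SAP 14.1: "Sum Total Composite Score is derived at each visit across the 3 biopsy sites for each subject". On the scale it says: "Assuming the subject had all 3 sites biopsied, the sum total composite score has a range of 0 to 36". With one or two sites missing, the composite is "calculated as the sum of the available scores which are then stretched/scaled to fit the 0-36 range". With no site scored, it stays missing. No rule links the sites used at the two visits, and no matched-site or complete-site sensitivity analysis is named.
- **Analysis.** SAP 14.1 gives descriptive statistics and "an ANCOVA analysis comparing the change values for each dose group vs. placebo", with the baseline composite as covariate.
- **General missing-data rule.** SAP 10.4 rules out imputation. The rescaling in SAP 14.1 is not reconciled with it.
- **Previous tests.** Protocol 10.4: "Any subject that as previously had a Syn-One Test™ does not need to have this procedure repeated". Site staff enter that result in the eCRF. No age limit is set, whereas Protocol 8.2 limits a historical MRI or CT scan to one year before screening.
- **Baseline and population.** SAP 10.2 takes the last non-missing value up to the first dose, with no earliest date. SAP 8 admits to the skin biopsy population any safety-population subject with a result.
- **Second biopsy.** Protocol 9.2.11 and the schedule of assessments place a biopsy at Day 182 / early termination. Protocol 10.4 gives timing only for the screening biopsy.

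**The concern.** Change is the difference between two composites. If they are built from different sites, the difference mixes change over time with differences between sites. Stretching the available sum fills a missing site with the mean of the available ones, which is harmless for change only if the lost site happens to score that mean.

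The ANCOVA in SAP 14.1 is the only planned treatment comparison for this objective. The same composite also enters the correlations with plasma biomarkers (SAP 13.2) and, at baseline, defines positive and negative subgroups (SAP 10.6 and 13.2). The sample is at most 40 per arm. It will be smaller if any subjects were randomised before the test was introduced or have reacted to local anaesthetic, since both groups are exempt (Protocol 10.4).

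A second, separate route concerns the time span. If a previous test serves as baseline, a change labelled as six months may cover a longer and unknown interval.

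**Working it through.** The plan gives no figure for this endpoint, so there is nothing to reproduce. The check applies the SAP rule to unchanged scores.

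**Inputs.** Three sites and a 0-36 total (SAP 14.1). Equal site ranges are assumed, giving 36/3 = 12 per site. The site scores below are illustrative; the documents give none.

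**Formulas.** Call the scores a, b, c, the same at both visits, with full composite a + b + c.
- Site c missing at end of study: composite = (a + b) x 36/24. False change = 1.5(a + b) - (a + b + c) = (a + b)/2 - c, the mean of the remaining sites minus the lost one.
- Only site a left: composite = a x 36/12. False change = 3a - (a + b + c) = 2a - (b + c).
- If the loss is at baseline instead, the sign reverses.

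**Example.** Cervical 8, thigh 4, leg 2; full composite 14 and no true change.

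| Available at end of study | Composite | False change |
|---|---|---|
| Cervical + thigh | 12 x 1.5 = 18 | +4 |
| Cervical + leg | 10 x 1.5 = 15 | +1 |
| Thigh + leg | 6 x 1.5 = 9 | -5 |
| Cervical only | 8 x 3 = 24 | +10 |
| Thigh only | 4 x 3 = 12 | -2 |
| Leg only | 2 x 3 = 6 | -8 |

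**Limits.** One site lost: 12/12/0 without the last goes from 24 to 36 (+12); the mirror case gives -12. Two lost: 12/0/0 with only the first goes from 12 to 36 (+24); the mirror case gives -24. Scores of 6/6/6 give 0. Over all 13 x 13 x 13 integer score triples, weighted equally (an assumption), the false change is non-zero in 96.1%. Its mean absolute size is 3.8 points with one site lost and 7.6 with two.

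**Matched sites.** If only cervical and thigh count at both visits, the score is 18 and 18, so change is 0. This holds for every pattern that leaves a shared site.

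**Within-arm mean.** With an assumed 25 subjects in an arm, three of whom lose the cervical site at end of study, the mean change moves by 3 x (-5)/25 = -0.60 points.

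**Arm comparison.** With baseline as covariate, the treatment estimate from change equals that from the end-of-study score. An error in the baseline therefore acts only through the covariate. An error at end of study enters the outcome, but cancels in expectation when missingness is unrelated to arm. What remains is noise:
- Let a fraction f of subjects lose one site at one visit, with between-site SD s and SD of true change d. If site means are equal, the variance of change is d² + f(s²/2 + s²) = d² + 1.5fs².
- Low case (f = 0.1, s = 2, d = 5): (25 + 0.6)/25 = 1.02. High case (f = 0.3, s = 4, d = 3): (9 + 7.2)/9 = 1.80. All of these values are assumed.
- In a simulation with no effect, assuming 30 per arm, site means 6/3/1.5 and a random site missing in 10% or 20% of subjects independently at each visit, mean bias was -0.02 and -0.03 and type I error 4.6-5.0%. The SD of the arm contrast was 0.96 with none missing, 1.04 at 10% and 1.13 at 20%.
- Matched-site scoring lowered that SD from 0.84 to 0.68 under one other set of assumed scores, and left it about equal under others.

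**Previous test as baseline.** Extra change = drift per year x years between the old test and study baseline. At an assumed 1-4 points per year and 0.5-3 years, it runs from 1 x 0.5 = 0.5 to 4 x 3 = 12 points. The documents give neither number.

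**The case against.** Scaling up from the available sites is pre-specified and a defensible choice. The three punches are one procedure, and the exemptions in Protocol 10.4 remove the whole procedure rather than one site, so partial loss may be rare. No document gives a missing-site rate, a gradient between sites or a per-site range. All of this stands, and it limits how large the problem can be said to be. It does not supply a matched-site rule.

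A reader might infer that a few mismatched subjects could dominate the difference between dose and placebo, or produce a false treatment effect. The documents do not support that. Under randomisation the false changes balance on average unless missingness, or the site that is lost, differs by arm, and nothing in the plan suggests that it would.

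A reader might also take it as settled that an old test becomes the baseline and creates a spurious effect. That reading rests on Protocol 10.4, SAP 10.2 and SAP 8 taken together; the SAP never mentions previous tests. Protocol 10.4 does not say that the three site-level scores are recorded or filed as baseline, and it could also be read as waiving the Day 182 biopsy, which would leave no change score. Even as baseline, an old test acts in the ANCOVA mainly as a noisier covariate. With 20% of baselines shifted by 4 points in the same kind of simulation, bias was 0.00, type I error 4.3%, and the SD 0.98 against 0.96. Descriptive change would still be affected, if pathology or the assay reading had moved in between.

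**Conclusion.** The point holds at subject level. A site scored at only one visit can create change with no change in any site score, by up to 12 points either way with one site lost and 24 with two, assuming 0-12 per site. If missingness is unrelated to arm, the consequence is distorted within-arm change and a less precise ANCOVA, not bias. How much depends on site differences and missing-site rates that the documents do not give. The endpoint is exploratory; the primary safety objective and the MoCA test are untouched.

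The previous-test issue is a weaker, separate point: an ambiguity to resolve and test by sensitivity analysis. It does not justify removing those subjects from the main analysis.

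**What to change.** Amend SAP 14.1 before unblinding:

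1. Derive change only from sites scored at both visits. Sum those sites at each visit, scale both sums by the same factor, and use the matched baseline as the ANCOVA covariate. Set change to missing when no site is shared.
2. Repeat the analysis in subjects with all three sites at both visits, as a sensitivity analysis.
3. State how the remaining rescaling stands against the no-imputation rule in SAP 10.4.
4. Reconcile Protocol 10.4 with Protocol 9.2.11 on whether a subject with a previous test still has the Day 182 biopsy, and state whether the earlier result may serve as baseline.
5. Flag subjects with a previous test, keep them in the main analysis, and repeat the descriptive change and the ANCOVA restricted to screening-period baselines.

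**Cost.** SAP wording, one derivation and two sensitivity runs, with no new data collection. Subjects with no shared site leave the change analysis, and scores from a site seen at one visit only go unused. Where sites score alike and visit-to-visit noise is large, that discarded information can cost a little precision.

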## 15. SAFETY ANALYSES

All safety analyses will be based on the safety population.

### 15.1 Adverse Events

All AE summaries will be restricted to treatment-emergent AEs (TEAEs), which are defined as those AEs that occurred on or after the date of first dose and those existing AEs that worsened during the study. If it cannot be determined whether the AE is treatment emergent due to a partial

onset date, then it will be counted as such. Verbatim terms in the eCRFs will be mapped to SOC and PTs using MedDRA.

Summary tables that are presented by relationship to investigational product will consider any TEAE that is assessed by the principal investigator as probably or possibly related to investigational product to be related to investigational product. TEAEs considered unlikely or not related to investigational product will be considered unrelated to investigational product in summary tables. TEAEs with a missing relationship will be considered related to investigational product in all summary tables.

Summary tables that are presented by severity will consider TEAEs with missing severity as having a severity of severe.

Each AE summary will be displayed by treatment group. Summaries that are displayed by SOC and PTs will be ordered by descending subject count in the total column by SOC and PT. Summaries of the following types will be presented:

- Overall summary of TEAEs that contains an overview of each of the following:
  - Subjects experiencing any TEAE and the total number of TEAEs
  - Subjects experiencing any TEAE considered related to investigational product and the total number of TEAEs considered related to investigational product
  - Subjects experiencing a treatment-emergent SAE and the total number of treatment-emergent SAEs
  - Subjects experiencing a treatment-emergent SAE related to investigational product and the total number of treatment-emergent SAEs related to investigational product
  - Subjects experiencing any TEAE with an outcome of death and the total number of TEAEs with an outcome of death
  - Subjects experiencing a TEAE with a severity of severe and the total number of TEAEs with a severity of severe
  - Subjects experiencing a TEAE with a severity of severe that is related to investigational product and the total number of TEAEs with a severity of severe that is related to investigational product
  - Subjects experiencing a TEAE leading to discontinuation of investigational product and the total number of TEAEs leading to discontinuation of investigational product
  - Subjects experiencing a TEAE related to investigational product leading to discontinuation of investigational product and the total number of TEAEs related to investigational product leading to discontinuation of investigational product

- Subjects experiencing a TEAE leading to discontinuation of study and the total number of TEAEs leading to discontinuation of study
- Subjects experiencing a TEAE related to investigational product leading to discontinuation of study and the total number of TEAEs related to investigational product leading to discontinuation of study

In addition to the overall TEAE summary the following summaries will be presented.

- Subject incidence of TEAEs and total number of unique TEAEs by MedDRA SOC and PT
- Subject incidence of TEAEs by MedDRA SOC, PT, and highest severity. At each level of subject summarization, a subject is classified according to the highest severity if the subject reported 1 or more events. AEs with missing severity will be considered severe for this summary.
- Subject incidence of TEAEs by MedDRA SOC, PT, and maximum relationship to study drug (related/not related). Related AEs are those reported as “Probable” or “Possible,” and unrelated AEs are those reported as “Unlikely” or “Not Related.” At each level of subject summarization, a subject is classified according to the maximum relationship if the subject reported 1 or more events. AEs with a missing relationship will be considered related for this summary.
- Subject incidence of serious TEAEs and total number of unique serious TEAEs by MedDRA SOC and PT
- Subject incidence of TEAEs leading to death by MedDRA SOC and PT
- Subject incidence of TEAEs leading to discontinuation of investigational product by MedDRA SOC and PT
- Subject incidence of TEAEs leading to discontinuation of study by MedDRA SOC and PT
- Subject incidence of non-serious TEAEs and total number of unique non-serious TEAEs by MedDRA SOC and PT

Separate listings of treatment-emergent AEs, treatment-emergent SAEs, AEs leading to death, and AEs leading to investigational product discontinuation will be presented.

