12.2 Adverse Events

12.2.1 Definitions

Adverse Event

An Adverse Event (AE) is any untoward medical occurrence in a subject or clinical investigation subject undergoing a study procedure or administration of a study drug. An AE can therefore be any unfavorable and unintended sign (including an abnormal laboratory finding), symptom, or disease temporally associated with the use of the study drug, whether considered related to the study drug or not.

Related Adverse Event

A related AE is an AE with a causality rating of “possible” or “probable”.

Not related Adverse Event

A not related AE is an AE with a causality rating of “unlikely” or “unrelated”.

Laboratory Abnormality

A laboratory abnormality is any clinically significant laboratory abnormality suggesting a disease or organ toxicity and which is of a severity requiring active management (i.e., changes of dose, discontinuation of drug, more frequent follow-up, medical treatment, or a diagnostic investigation). Laboratory abnormalities are also considered AEs, if clinically significant.

Pretreatment Adverse Events

A pretreatment AE is any AE occurring during the pretreatment period (between informed consent and initiation of a study drug).

Post-study Adverse Event

A post-study AE is an AE occurring up to 30 days after the treatment period.

Treatment-emergent Adverse Events

Treatment-emergent adverse events (TEAEs) are all AEs occurring during the treatment period or a pretreatment AE that worsens in intensity during the treatment period.

Treatment Period

The treatment period is the period during which a subject receives study drug (i.e., first dose through last dose).

Serious Adverse Event

A serious adverse event (SAE) is any untoward medical occurrence that results in death, is life-threatening, requires in-patient hospitalization or prolongation of existing hospitalization, results in persistent or significant disability/incapacity, is a congenital anomaly/birth defect observed in any offspring of the subject conceived during treatment with the study drug or is an important medical event. See Section 14 for more details on SAEs.

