12.2.3 Adverse Event Follow-up

Adverse events requiring therapy must be treated with recognized standards of medical care to protect the health and well-being of the subject.

Any subject who has any AE (whether serious or non-serious) or clinically significant (in the Investigator's opinion) abnormal laboratory test values will be evaluated by the Investigator or a monitoring physician and will be treated and followed up until the symptoms or values return to normal or acceptable levels, as judged by the Investigator and the Sponsor.

Adverse events that are unresolved at end of study or upon early withdrawal will be tracked at least weekly by site staff until resolution, for 30 days, or until the subject is lost to follow-up (defined as failure to respond to three phone messages left on separate days and one certified letter requesting follow-up).

Subjects will be instructed to inform site staff of any AEs occurring during the 30-day period after discharge or early withdrawal.

Any follow-up information available at the time of the subject's end of study will be included in the clinical study report.

Any SAE that is considered to be unexpected and related to the study drug occurring after the end of study should be forwarded to the Sponsor. These cases will be handled and submitted as expedited reports but will not be included in the clinical study report.

Note: Any SAE will be reported to NIH by the sponsor within 48 hours of the time when the Sponsor becomes aware of the event.

13 Serious And Other Significant Adverse Events

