## 16. CHANGES TO PROTOCOL-SPECIFIED ANALYSES

The following analyses in this SAP are different from Protocol version 3.0.

- The following analysis populations are included in this SAP but are not defined in the protocol: enrolled population, completers/compliers population, skin biopsy population. These populations have been added in order to facilitate summaries of data using applicable subject subsets of data.

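### SAP 15.1 sets no end to the treatment-emergent AE window, so about 28 off-drug days enter every AE table, contrary to the protocol and undeclared in SAP 16

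*SAP*

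**What the plan says.** Section 15.1 of the SAP states: "All AE summaries will be restricted to treatment-emergent AEs (TEAEs". It describes these as "defined as those AEs that occurred on or after the date of first dose and those existing AEs that worsened during the study". The window opens on a calendar date and is given no close.

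Protocol 12.2.1 uses a closed window. "Treatment-emergent adverse events (TEAEs) are all AEs occurring during the treatment period or a pretreatment AE that worsens in intensity during the treatment period". The period itself is also defined: "The treatment period is the period during which a subject receives study drug (i.e., first dose through last dose". Events on either side have their own classes. Before dosing: "A pretreatment AE is any AE occurring during the pretreatment period (between informed consent and initiation of a study drug". After dosing: "A post-study AE is an AE occurring up to 30 days after the treatment period".

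Three other places in the SAP bear on the point:

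- Appendix A, on incomplete dates, treats an event as treatment-emergent when it is assumed to fall in the treatment phase of the study.
- Section 15.2 ends duration of treatment at the last dose date.
- Section 16 opens its list of departures with "The following analyses in this SAP are different from Protocol version 3.0" and then names only added analysis populations.

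**The concern.** Safety and tolerability is the primary objective, and a single flag decides what appears in every AE table. Under the SAP wording that flag also takes in events that begin after drug has stopped, which the protocol assigns to a different class. The two documents therefore give different counts from the same data, and the SAP does not say so.

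Three consequences follow. Off-drug background events are added to each arm, which tends to blur a contrast between active and placebo if the drug acts only while it is taken. Section 15.2 reports exposure to the last dose while section 15.1 counts events beyond it, so numerator and exposure cover different periods. And no planned table lets a reader see on-drug and post-drug events separately by arm.

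There is also a programming risk. Appendix B of the SAP requires two independently programmed datasets to match completely. A programmer who follows 15.1 and one who follows Appendix A or the protocol would set the flag differently for the same post-dose event.

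**Working it through.** **Timeline.** The documents give no figure for the AE window itself. The nearest stated figure is the maximum participation of 254 days, which reproduces as 42 (screening) + 210 + 2 (visit window) = 254. Day 210 is thus the last planned visit.

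**Inputs.**

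- Dosing runs through Day 182 (Protocol 7.2).
- AEs are collected from consent until the follow-up visit (Protocol 12.2.2), about 28 days after treatment for subjects who complete Day 182 (Protocol 5.3).
- SAEs are reported to 30 days after last treatment (Protocol 13.1.1).
- Early stoppers have a visit within 14 days of the last dose (Protocol 8.5.1).

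**Definitions side by side.**

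| Element | Protocol 12.2.1 | SAP 15.1 |
|---|---|---|
| Start | initiation of drug | date of first dose |
| End | last dose | none stated |
| Worsening judged over | treatment period | whole study |
| Onset on Day 205, last dose Day 182 | post-study AE | TEAE |

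**Off-drug time for a completer.** 210 − 182 = 28 days. Relative to the protocol window, 28/182 = 15.4%. As a share of the SAP window, 28/210 = 13.3%. With the 30-day SAE period instead, 30/212 = 14.2%.

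**Off-drug time for an early stopper**, with a 14-day gap to the early termination visit: 14/42 = 33% if the last dose is on Day 28, 14/70 = 20% for Day 56, and 14/112 = 12.5% for Day 98.

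**Effect on incidence.** The documents give no AE rate, so the on-drug incidence p is an assumption, shown over a range, with constant hazard on and off drug. Incidence to Day 210 is 1 − (1 − p)^(210/182).

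| p to Day 182 | To Day 210 | Extra subjects per 40 |
|---|---|---|
| 30% | 33.7% | 1.5 |
| 50% | 55.1% | 2.0 |
| 70% | 75.1% | 2.0 |
| 90% | 93.0% | 1.2 |

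**Effect on the contrast between arms.** Assume a background rate of 0.5 events per 182 days, doubled by drug only while it is taken.

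- To Day 182: placebo 1 − exp(−0.5) = 39.3%; active 1 − exp(−1.0) = 63.2%; difference 23.9 points.
- The 28 off-drug days add 0.5 × 28/182 = 0.077 to each exponent: placebo 43.8%, active 65.9%, difference 22.1 points.
- The change is 1.8 points, about 0.7 of a subject per arm of 40.

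**The case against.** Counting follow-up events in the main AE tables is a common and cautious choice, and the same rule applies in every arm. Protocol 14.4.2 plans AE summaries without limiting them to the treatment period, so a broad window is not foreign to the protocol. The practical effect is bounded because routine collection stops at the follow-up visit. The SAP plans counts and subject incidence, with no AE rate ratio or test, and the shift in incidence is small. Subject-level listings keep every onset date. All of this stands. It limits the weight of the point but does not remove it: the SAP restricts its tables to a term that the protocol defines differently, gives no end date, and leaves the difference out of section 16. Listings do not replace a summary by arm.

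A reader might infer more than the documents support:

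- **Window to Day 240.** Protocol 12.2.3 says: "Subjects will be instructed to inform site staff of any AEs occurring during the 30-day period after discharge or early withdrawal". But 12.2.2 ends routine collection at the follow-up visit, and 12.2.3 keeps even unexpected, related SAEs after the end of study out of the study report. About Day 210 is the supportable bound.
- **Off-drug follow-up for completers only.** Early stoppers miss the Day 210 visit, but they have a visit within 2 weeks of the last dose, the 30-day instruction just quoted, and SAE reporting to 30 days.
- **Worsening before dosing counted as treatment-emergent.** The SAP wording would allow it, but note 28 to Table 1 limits collection in screening to procedure-related SAEs, so few such cases should exist. Protocol 12.1.1 and 12.2.2 are worded more broadly.
- **Day 1 pre-dose events as a material error.** Protocol 12.2.2.1 defines onset by date. Without a recorded time or a pre-dose flag, neither definition can separate them, and less than one day per subject is involved.

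**Conclusion.** The point holds as an undeclared conflict between the SAP and the protocol over where the treatment-emergent window ends, together with a mismatch over the period in which worsening is judged. The SAP is also not consistent within itself.

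For a completer, about 28 off-drug days, 15% on top of 182, enter every AE table. Under a constant hazard that is about 1 to 2 extra subjects per arm of 40. The effect on a between-arm difference is under one subject per arm in the example above. The window lengths come from the documents; the AE rates are assumptions. Dilution further assumes no delayed or withdrawal effects. A reader might conclude that the safety comparison is badly distorted, and these figures do not show that.

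The reason to act is that one flag drives all the AE tables for the primary objective, and as planned they cannot show which events arose on drug. The change should be made, but it is not critical to the trial.

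**What to change.** Amend SAP 15.1 before unblinding, in one of two ways.

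1. Adopt the protocol's window: onset, or worsening of a pretreatment AE, from first dose through last dose. Summarise AEs with onset after the last dose in a separate post-treatment table by arm.
2. Keep a longer window, but give it an explicit end relative to the last dose, declare it in SAP 16, and show an on-treatment table beside it.

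In either case, judge worsening over the treatment period rather than the study as a whole, and bring Appendix A into line. State that AEs dated Day 1 count as treatment-emergent by date unless a time or pre-dose flag shows otherwise.

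The cost is SAP wording, one derived flag and one added table, with no new data collection. Under the first option TEAE counts become slightly smaller, and the removed events appear in the post-treatment table.
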